6. STUDY DESIGN

6.1 General study design and justification of design

The ESTxENDS trial is a multicentre, pragmatic, open-label randomized controlled trial with two parallel groups allocated in a 1:1 ratio. The trial will assess superiority of ENDS + SCC for smoking cessation to SCC alone in adult (≥ 18 years) smokers. The intervention group will receive ENDS and nicotine-containing e-liquids to use ad libitum, plus SCC. The control group will receive SCC only. At the end of the 6 months, participants in the control group will receive a voucher ("BERNcity Geschenkkard") worth CHF30 in order to maximize retention of participants in the control group. A total of 1172 smokers will be included in the study, 586 in each group. Recruitment of the participants is planned to occur over 13-18 months at all 3 study sites. Our main outcome will be self-reported continuous smoking cessation after target quit date over a 6-month follow-up period, with blinded biochemical verification by exhaled carbon monoxide (CO), urinary cotinine, anabasine, VOCs, TSNAs (NNN, NNK and its metabolite NNAL) and PAHs (1- and 2-Naphtol and 1-OHP) levels. Statisticians and laboratory personnel will be blinded to group allocation. Participants and clinicians will not be blinded. We will use the methodology of clinical trial investigating a medicinal product to test the efficacy and safety of ENDS. We will mimic the methods of a pharmacovigilance and safety study.

Figure 6.1-1: ESTxENDS trial design schematic

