5. STUDY OUTCOMES

5.1 Primary Outcome

The primary outcome for the main analysis at 6-months follow-up will be the continuous smoking abstinence from target quit date (TQD) to the 6-month follow-up visit, ascertained by self-report (self-report of no smoking from target quit date) and confirmed by urinary level of anabasine (<3 ng/ml).^{1, 34, 35} If anabasine is missing, validation will be done by exhaled carbon monoxide (CO) (<10 ppm).

The primary outcome for the extended follow-ups at 12- and 24-months will be the self-reported 7-day point prevalence abstinence (not having smoked cigarettes within the preceding week), again confirmed by urinary level of anabasine (<3 ng/ml). If anabasine is missing, validation by exhaled carbon monoxide (CO) (<10 ppm).

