6.2.2 Blinding procedures

Participants, nurses and investigators will not be blinded. We will blind both the statisticians who perform the main analyses and the laboratory personnel who determine urinary cotinine, anabasine, VOCs, TSNA (NNN, NNK and its metabolite NNAL) and PAHs (1- and 2-Naphtol and 1-OHP) levels.

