9.2 Assessments of outcomes

Participants will be seen in a healthcare facility in each center four times, at baseline, after 6-, 12- and 24- months. Data will be collected by study nurses, supervised by the responsible investigator at each site, based on protocols standardized across sites. All data will be directly collected via centralized computerized data entry forms. Laboratory analyses of urine samples will be centralized at the laboratory in Lausanne (Unisanté, Centre universitaire de médecine générale et santé publique, Lausanne). The laboratory is accredited ISO 17025 for nicotine quantification in urine, VOCs quantification, and it will use validated methods for the other compounds in urine and oxidative stress analyses. The samples are only stored and continued to be used with the participants consent independent from the study (see section 12.6). The blood samples from which analysis of blood lipids, HbA1c (only for participants with diabetes), creatinine will be performed, will remain in the main laboratory of each health center. The other blood sample for the analyses of inflammatory biomarkers from the centers in St. Gallen and Bern will be transported and stored in the biobank in Bern. Blood samples from participants in Geneva are stored at the local biobank in Geneva. Analyses of exhaled breath condensates will only be performed in Lausanne and thus centralized at the laboratory in Lausanne (Unisanté, Centre universitaire de médecine générale et santé publique, Lausanne). CTU Bern personnel will monitor quality. We will inform participants that some random phone calls will be recorded for quality monitoring. Quality monitoring will include reviewing calibration procedures for carbon monoxide (CO) and blood pressure measuring devices, weight and height scales.

The table below shows which outcome markers listed in 9.1 are collected in which center:

Tobacco use (questionnaires)	Bern, Geneva, Lausanne, St. Gallen, Zürich
Estimated ENDS use (ml e-liquids used)	Bern, Geneva, Lausanne, St. Gallen, Zürich
Exhaled CO	Bern, Geneva, Lausanne, St. Gallen, Zürich
Urinary nicotine, cotinine, anabasine	Bern, Geneva, Lausanne, St. Gallen, Zürich

Urinary metabolites of nitrosamines (TSNAs)	Bern, Geneva, Lausanne, St. Gallen, Zürich
Adverse events, serious adverse events	Bern, Geneva, Lausanne, St. Gallen, Zürich
VOC and PAH metabolites in urine	Bern, Geneva, Lausanne, St. Gallen, Zürich

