9.2.2 Assessment of secondary outcomes

The secondary outcomes will be measured as described for the primary endpoint.

Secondary smoking cessation outcome will be measured with a self-reported 7-day point prevalence abstinence (not having smoked cigarettes within the preceding week), again confirmed by urinary level of anabasine, and change in the self-reported number of cigarettes smoked per day (CPD) with 50% reduction in CPD from baseline to follow-up considered as successful reduction, measured as above.

For alternate validation methods of the primary and secondary outcomes, we will use CO-levels, which will be measured with a Micro Smokerlyser®; Bedfont Scientific Ltd.

Respiratory symptoms will be assessed by questionnaires:

- COPD Assessment Test (CAT), Modified Medical Research Council (MMRC) Scale, Asthma Test (ACT/ ECRHS)

Each Urine sample will be split into six aliquots to quantify cotinine and anabasine (see above), PAH metabolites, VOCs, propylene glycol, TSNAs, 8-OHdG and 8-isoprostanes, since no analytical method can measure all the compounds together. The different compounds will be estimated as follows:

- Concentrations of urinary cotinine and anabasine, VOCs, TSNAs and PAHs will be measured
- Oxidative stress will be assessed by quantifying 8-OHdG and 8-isoprostane concentrations in both EBC and urine
- We will adapt the method for analyzing urinary TSNAs from Xia et al.³⁰ After enzymatic hydrolysis with a β -glucuronidase solution, the urine sample will be extracted using solid phase extraction (SPE) columns, and analyzed by LC/MS/MS.
- We will use a high performance liquid chromatography (HPLC) method developed by the IST laboratory to analyze PAHs (1- and 2-Naphthol and urinary 1-OHP).

Exhaled breath condensates (EBC) other than CO will be performed in all participants at the Lausanne site during the first as well as the outcome visit (baseline and 6 months), based on guidelines from the American Thoracic Society (ATS)/European Respiratory Society (ERS) Task Force for EBC collection⁸⁷. EBC will be sampled with an EcoScreen II system (total exhaled volume of about 120 L). After collection, each sample will be aliquoted. To avoid auto-oxidation of fatty acids (potential impact on 8-isoprostane levels), we will add tert-butyl hydroxytoluene and rapidly freeze the sample. The samples will be stored at -70°C for a maximum of 1 month.⁹⁰

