6.1 Outcome definitions

Primary outcome: The primary outcome will be the continuous cigarette smoking abstinence from target quit date to the 6-month follow-up visit, ascertained by self-report at the 6-month follow-up exam (self-report of no smoking from target quit date) and confirmed by urinary level of anabasine (<3 ng/ml). If anabasine is missing, validation by exhaled carbon monoxide (CO). The outcome is a binary outcome.

Core secondary outcomes:

- Secondary smoking cessation outcomes to the 6-month follow-up visit:
 - Continuous smoking abstinence. Self-report of having smoked no cigarettes from TQD, validated by urinary levels of NNAL (4-(methylnitrosamino)-1-(3-pyridyl)-1-butanol). If NNAL is missing, validation by urinary levels of anabasine or exhaled CO.
 - Self-reported smoking abstinence allowing a 2-week 'grace period' after the TQD
 - Validated smoking abstinence allowing a 2-week 'grace period' after the TQD, validated by urinary levels of anabasine. If anabasine is missing validation by exhaled CO.
 - Validated smoking abstinence allowing a 2-week 'grace period' after the TQD, validated by urinary levels of NNAL. If NNAL is missing, validation by urinary levels of anabasine or exhaled CO.
 - Self-reported smoking abstinence allowing up to 5 cigarettes in total after the TQD.
 - Validated smoking abstinence allowing up to 5 cigarettes in total after the TQD, validated by urinary levels of anabasine. If anabasine is missing validation by exhaled CO.
 - Validated smoking abstinence allowing up to 5 cigarettes in total after the TQD, validated by urinary levels of NNAL. If NNAL is missing, validation by urinary levels of anabasine or exhaled carbon monoxide (CO).
 - Self-reported 7-day point prevalence abstinence at 6 months, Self-report of having smoked no cigarettes in the past seven days.
 - Validated 7-day point prevalence abstinence. Confirmation of having smoked no cigarettes in the past seven days, validated by urinary levels of anabasine. If anabasine is missing validation by exhaled carbon monoxide (CO).
 - Validated 7-day point prevalence abstinence. Confirmation of having smoked no cigarettes in the past seven days, validated by urinary levels of NNAL. If NNAL is missing, validation by urinary levels of anabasine or exhaled carbon monoxide (CO).

CTU Bern	SAP for: ESTxENDS	Version: 4.02.0	
CTU Bern	Template: Statistical Analysis Plan (SAP)	Version: 03	
	Code: CS_STA_TEM-11	Valid from: 28.02.2019 to 06.2023	Page 18 of 27

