6.2 Derivation of Outcomes

Comments to secondary smoking cessation outcomes:

- Smoking is allowed during the grace period.
- The number of cigarettes smoked since the last visit is recorded as a categorical variable (1-5 cigarettes, >5 cigarettes). If the participant smoked more than once a day cigarettes in the last 7 days, the value is recorded as numeric variable. For secondary smoking cessation outcomes, we will assume the median value for the categorical variable. I.e. if a subject records 2 times to smoke 1-5 cigarettes, we assume him to be over the limit of 5 cigarettes.

Table 3: Derivation of primary and secondary outcomes.

Outcome	eCRF sheet	Variable	Variable type	Derivation	Outcome type
Primary: continuous smoking abstinence from target quit date to the 6-month follow-up visit AND	cig_ecig	quit_smoke_again	Binary: No, Yes	{ [Week 1/2/4/8, and month 6] quit_smoke_again == No AND quit_tobacco_inhale ==	Binary
		quit_tobacco_inhale	Binary: No, Yes		
	cig_ecig_6m	quit_smoke_again	Binary: No, Yes		
		quit_tobacco_inhale	Binary: No, Yes		

CTU Bern	SAP for: ESTxENDS	Version: 1-02.0
-----------------	-------------------	---------------------------------

CTU Bern	Template: Statistical Analysis Plan (SAP)	Version: 03
	Code: CS_STA_TEM-11	Valid from: 28-02-2019 to 05-06-2023

urinary level of anabasine (<3 ng/ml) OR	to be defined	to be defined	to be defined	No} AND {x < 3 if x!=missing, vs_co2_level<10 if x==missing & vs_co2_level ==missing}
CO level	vital_6m	vs_co2_level	Continuous	
Secondary outcomes				
continuous smoking abstinence from target quit date to the 6-month follow-up visit AND	Cig_ecig, cig_ecig_6m	quit_smoke_again, quit_tobacco_inhale	Binary: No, Yes, Binary:No, Yes	{[Week 1/2/4/8, and month 6] quit_smoke_again == No AND quit_tobacco_inhale == No} AND
urinary level of NNAL (<10 pg/ml creat) OR	To be defined	To be defined	To be defined	{y < 10 if y!=missing, x<3 if y==missing & x!=missing, vs_co2_level<10 if y==missing & x==miss- ing & vs_co2_level!=missing }
urinary level of anabasine (<3 ng/ml) OR	To be defined	To be defined	To be defined	
CO level	Vital, Vital_6m	vs_co2_level	continuous	
Continuous smoke abstinence allowing a 2-week grace period after TQD	cig_ecig / cig_ecig_6m	quit_smoke_again quit_tobacco_inhale	Binary: No, Yes	[Week 4, Week 8, and 6 months] sum(quit_smoke_again == No) >= 2 AND sum(quit_tobacco_in- hale == No) >= 2

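### Protocol 9.0 describes exhaled-CO verification of the main outcome as blinded, but nothing in the design blinds CO, which alone confirms abstinence when anabasine is missing

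*Supplement*

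**What the plan says.** Protocol 9.0, 6.1 describes the 6-month main outcome as self-reported continuous abstinence "with blinded biochemical verification by exhaled carbon monoxide (CO), urinary cotinine, anabasine, VOCs" and further urinary markers. CO stands first in that list.

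Protocol 9.0, 6.2.2 then says "Participants, nurses and investigators will not be blinded". The measurement staff it does blind are "the laboratory personnel who determine urinary cotinine, anabasine, VOCs, TSNA" and the other urinary markers; CO is not mentioned. SAP 2.0, 2.8 narrows laboratory blinding to the urinary metabolites of nicotine.

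On who measures, Protocol 9.0, 9.2 says "Data will be collected by study nurses, supervised by the responsible investigator at each site". On how, 9.2.2 says "we will use CO-levels, which will be measured with a Micro Smokerlyser", a breath device. The schedule in 9.1 places exhaled CO at the baseline and outcome visits, and SAP Table 3 takes the value from the 6-month vital-signs form.

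On the role of CO, Protocol 9.0, 5.1 says "If anabasine is missing, validation will be done by exhaled carbon monoxide (CO) (<10 ppm"; SAP 2.0, 6.1 has the same rule: "If anabasine is missing, validation by exhaled carbon monoxide (CO". CO is also a fallback in the validated secondary cessation outcomes.

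**The concern.** In an open-label trial with a self-reported outcome, biochemical verification is the main guard against arm-dependent reporting, and blinding that verification is a property readers will rely on. SAP 2.0 has dropped blinding of the statisticians (2.8 and Table 4), so the blinded urine assay is the main blind step left between self-report and outcome.

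In Protocol 2.0, CO was required together with the urine markers and could not confirm a quit by itself. Protocol 9.0 and the SAP give it that role when anabasine is missing, while 6.1 keeps the word blinded. For participants confirmed by CO alone, no step from self-report to classification is blinded. The share of such participants could also differ by arm: the history of protocol changes records selective withdrawal in the control group. That makes arm-dependent gaps in urine samples plausible, though it does not show them. The trial could then report a blinded verification that its procedures do not provide for every participant.

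**Working it through.** **1. Is CO blinded anywhere?** Setting the passages side by side:
- Protocol 9.0, 6.1: CO is in the blinded list.
- Protocol 9.0, 6.2.2: nurses and investigators are unblinded; only laboratory work on urinary analytes is blinded.
- SAP 2.0, 2.8: laboratory blinding covers urinary nicotine metabolites; CO is not named.
- Protocol 9.0, 9.2 and 9.2.2: nurses collect the visit data, and CO is a breath-device reading.

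No section describes a blinded CO reading or names a blinded person who could take it. That a nurse takes it is an inference from 9.2, but no other role is offered.

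**2. For whom does CO decide?** Three conditions must hold: self-reported abstinence, anabasine missing, CO present. If CO is missing too, SAP 6.5 counts the participant as a smoker.

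**3. The plan's own figure.** Inputs from Protocol 9.0, 11.2: 12% against 19%, two-sided alpha 0.05, power 90%. With unpooled variance, n = (1.960 + 1.282)² × (0.12 × 0.88 + 0.19 × 0.81) / 0.07² = 557 per group, as stated. Recruitment is 586 per group (1172 in total).

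**4. How much of the outcome could rest on CO alone?** The share q of attenders without anabasine is not in the documents; 2%, 5% and 10% are assumed. Claimed quitters are set at the planned rates.

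| q | Without anabasine per arm (557 × q) | ENDS quitters on CO alone (× 0.19) | Control quitters on CO alone (× 0.12) | ENDS, points (÷ 586) | Control, points (÷ 586) |
|---|---|---|---|---|---|
| 2% | 11 | 2.1 | 1.3 | 0.36 | 0.23 |
| 5% | 28 | 5.3 | 3.3 | 0.90 | 0.57 |
| 10% | 56 | 10.6 | 6.7 | 1.81 | 1.14 |

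These are ceilings. They would equal the error in an arm only if every CO-only confirmation there were false.

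**5. What bias might follow?** Let f be the share with CO but no anabasine, s the share of an arm falsely reporting abstinence, and m the share of those passed in the ENDS arm only because the reading was unblinded. The bias in the risk difference is f × s × m, with all three values assumed:
- f = 5%, s = 5%, m = 50%: 0.05 × 0.05 × 0.50 = 0.125 points.
- f = 10%, s = 5%, m = 50%: 0.25 points.
- f = 20%, s = 5%, m = 100% (extreme): 1.0 point.

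With a true rate of 12% in both arms and 586 per arm, the chance of a false finding in favour of ENDS rises from 2.5% to about 2.9%, 3.4% and 7.5% respectively.

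**6. Would a planned analysis show it?** The available-case analysis (SAP 6.3.3) and the censoring weights (SAP 6.5) deal with missing outcomes. The per-protocol analysis (SAP 6.3.2) deals with adherence and visit timing. The NNAL-validated secondary outcome still falls back on anabasine or CO. None isolates CO-only confirmations, and no section promises their count by arm.

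**The case against.** The strongest reply is that this is one loose phrase in a summary paragraph. The same paragraph of 6.1 says that participants and clinicians are unblinded, 6.2.2 lists only urinary analytes, and SAP 2.8 never claims a blinded CO. A careful reader can work out the true position. That stands as a reason to rate the point as minor. It does not remove the contradiction, because 6.1 is where the property of the main outcome is stated.

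The affected group is also likely to be narrow. Urine and CO are both collected at the 6-month visit, and contacts moved to the telephone during the pandemic would be expected to lack both and so count as smokers. NNAL-validated abstinence gives a partial cross-check.

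Three stronger readings are tempting and should not be drawn:
- **That CO-confirmed participants have no protection against bias.** CO is a numerical device reading against a fixed cut-off, so it still tests the self-report.
- **That the nurse who counselled the participant takes the breath right after hearing the self-report and may repeat a borderline one.** The documents fix neither the order of procedures nor who does which, and do not mention repeated breaths.
- **That up to 1.8 points of the effect is bias.** That figure is the part of the ENDS quit rate resting on CO alone at an assumed 10% without anabasine.

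**Conclusion.** The point holds, as a minor one. Protocol 9.0 section 6.1 claims blinding for a measurement that the design leaves unblinded, and that measurement alone confirms the primary outcome for self-reported abstainers with a CO value but no anabasine.

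Its size cannot be fixed from the documents. Under assumed missingness of 2 to 10%, at most about 0.4 to 1.8 points of the ENDS quit rate and 0.2 to 1.1 points of the control rate rest on CO alone. Under moderate assumptions the bias is 0.125 to 0.25 points, and 1.0 point in a deliberately extreme case, against a planned difference of 7 points. The conclusion rests on the inference that nurses take the CO reading and on the assumed values of q, f, s and m. It gives no ground to think that the primary result would be overturned.

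**What to change.** - **Protocol 6.1:** limit blinded to the urinary markers and state that exhaled CO is read unblinded. Since SAP 2.8 leaves laboratory staff unblinded for VOCs, PAHs and TSNAs, the safest wording names the nicotine-related markers, cotinine and anabasine, on which both documents agree.
- **SAP 6.3.3:** add one sensitivity analysis of the primary outcome in which only anabasine below 3 ng/ml confirms abstinence and CO-only confirmations count as not confirmed. Report by arm the number confirmed by CO alone.
- **At the same time, reconcile the CO rule.** SAP Table 3 codes the fallback for the primary outcome as "vs_co2_level<10 if x==missing & vs_co2_level ==missing", which applies the cut-off when CO itself is missing. The NNAL rows use the opposite condition, so this looks like a slip. The synopsis and 9.2.1 of Protocol 9.0 omit the fallback altogether.

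The main change costs one phrase and one extra line of analysis, with a count per arm, on data already collected. The stated property of the outcome becomes slightly less favourable.

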6.2 Methods of minimising bias

6.2.1 Randomisation

We will use a centralized computed randomization process to randomize participants into the intervention and control arm at a 1:1 ratio. The central server will be located in a protected environment

at CTU Bern.

6.2.2 Blinding procedures

Participants, nurses and investigators will not be blinded. We will blind both the statisticians who perform the main analyses and the laboratory personnel who analyse urinary cotinine, anabasine, VOCs, TSNAs (NNN, NNK and its metabolite NNAL) and PAHs (1- and 2-Naphtol and 1-OHP) levels.

6.2.3 Other methods of minimising bias

To minimize bias of safety outcomes, all clinical events (hospitalizations) and other serious adverse events will be verified by a blinded external committee whenever possible (see 1.7.3).

6.3 Unblinding Procedures (Code break)

Not applicable.

7. STUDY POPULATION

7.1 Eligibility criteria

Subjects fulfilling all of the following inclusion criteria are eligible for the study:

- Informed Consent as documented by signature
- Age 18 or older
- Currently smokes 5 or more cigarettes per day, for a least 12 months
- Willing to try to quit smoking within the next 3 months
- Persons providing a valid phone number, a valid email address and/or a valid postal address.

The presence of any one of the following exclusion criteria will lead to exclusion of the subject:

- Known hypersensitivity or allergy to contents of the e-liquid
- Participation in another study with investigational drug within the 30 days preceding the baseline visit and during the present study where interactions are to be expected
- Women who are pregnant or breast feeding
- Intention to become pregnant during the course of the study
- Persons having used ENDS regularly in the 3 months preceding the baseline visit
- Persons having used nicotine replacement therapy (NRT) or other drug therapy helping smokers quit (varenicline, bupropion) within the 3 months preceding the baseline visit
- Plans to move out of the country within the next 6 months, or cannot attend the 6- month follow-up visit for any reason
- Cannot understand instructions delivered in person or by phone, or otherwise unable to participate in study procedures

7.2 Recruitment and screening

Target population of the study are individuals who smoke 5 or more cigarettes/day since more than one year and are willing to try and quit within the next three months. Individuals will be recruited through media advertisements or directly at the study sites when seeking help for smoking cessation. Interested smokers will be screened over the phone by a trained nurse to review eligibility criteria. Smokers will also announce their target quit date and, if eligible and if they have no contra-indications for participating in the study, will be sent a participant information sheet and the informed consent form. The baseline visit will be scheduled a week before the quit date they named over the phone. At the baseline visit, trained study nurses will again verify the eligibility criteria, explain the trial and have participants sign the informed consent form.

